### **12.8.3 Other Efficacy Analyses**

Change from baseline in DLQI, PSD, SF-36, and Peak Pruritus-NRS will be analyzed using an ANCOVA model with treatment as a main effect, baseline PGA score as a categorical covariate, and baseline value of the endpoint as a covariate. Percent change from baseline in DLQI, PSD and Peak Pruritus-NRS will be summarized and analyzed using the same method.

In addition, the proportion of subjects with at least a 4-point reduction from baseline in the Peak Pruritus-NRS among subjects with a baseline NRS score  $\geq 4$  will be summarized and analyzed following the same method as the dichotomized secondary endpoints. A plot will be used to illustrate this information.

Subject itch diary and in-clinic itch score assessments will be listed and summarized using descriptive statistics by day. If a subject completed diary itch score on the date of in-clinic visit, the itch score assessed in-clinic will be used in the summary. Change from baseline, treatment difference (Tapinarof cream 1% – Vehicle Cream) in mean change from baseline values and its associated 95% CI will be summarized by day. In addition, the treatment difference and its associated 95% CI will be plotted by day.

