^d Medical history will include year of plaque psoriasis diagnosis, CV medical history and risk factors (including height, weight, smoking history, medical conditions, and family history of premature CV disease) and family history of liver disease.

^e Record any changes to medical history.

^f Serum pregnancy test to be performed at the Screening visit only and urine pregnancy test to be performed at subsequent clinic visits.

^g Urine pregnancy test to be performed before randomization.

^h Physical examination will include height, weight, and BMI at the Screening visit; a brief physical examination will be performed at other visits (Section 6.3.2).

- ⁱ Vital signs will include blood pressure, pulse, and body temperature.
- ^j Including serum chemistry and liver chemistry tests, and hematology.
- ^k Photography will be performed in a subgroup of subjects at selected (8 to 10) study centers; this is not required of subjects for participation in the study. Informed consent/assent and photographic release will be required.
- ^l Blood sample collection for PK will be performed at a subset of sites in a subset of subjects. Sample to be collected prior to study drug application in clinic.
- ^m The PGA assessment should be performed before the %BSA and PASI assessments.
- ⁿ The subject's scalp, palms, fingernails toenails, and soles should be excluded from the %BSA calculations.
- ^o %BSA affected calculation should be completed before the PASI assessment. Note that lesions on scalp, palms, fingernails, toenails, and soles will not be included in the calculation of %BSA affected as these areas will be excluded from the efficacy analyses.
- ^p The LTS assessment also consists of a subject-assessed component (Section [6.3.5](#)).
- ^q Subjects should perform the Peak Pruritus NRS assessment daily (Section [6.2.2.4](#)) and record the results in their diary. On study visit days, subjects will not complete the diary at home; application time and NRS will be recorded in the clinic.
- ^r Subjects will be instructed on when and how to complete diaries.
- ^s Subjects will be instructed to apply study drug once daily at the approximate same time each day, based on subject preference (Section [5.1.5](#)).
- ^t At clinic visits, study drug will be applied after safety and efficacy assessments have been conducted (see Section [5.1.5](#) for additional details on timing of application of study drug during clinic visits).

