### **11.3 Baseline and Change from Baseline**

Baseline value is defined as the last non-missing value prior to the first dose of study drug. Change from baseline is defined as the post-baseline value minus the baseline value unless otherwise specified. Percent change from baseline is calculated as follows: Percent change = (Change from baseline / Baseline) \* 100.

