## 12.8 Efficacy Analyses

All efficacy outcomes will be analyzed in the ITT population. Only the primary and secondary efficacy endpoints will be analyzed in the PP population as supportive analyses, as summarized in the Table below.

Efficacy Endpoints	Primary	Sensitivity Analysis
--------------------	---------	----------------------

	Analysis	
Primary Endpoint 
 
PGA response at Week 12
 
	ITT, MI	ITT, OC ITT, TF ITT, LOCF PP, OC
Secondary Endpoints Categorical Endpoint: 
 
PASI-75 at Week 12
 
PGA 0 or 1 at Week 12
 
PASI-90 at Week 12
 
 Continuous Endpoint: 
 
Change in %BSA at Week 12
 
	ITT, MI	ITT, OC ITT, TF (categorical endpoint) ITT, LOCF PP, OC
Exploratory Endpoints 
 
Time to PGA response
 
	ITT, OC	N/A
Exploratory Endpoints 
 
PGA 0 or 1 at Weeks 2, 4, and 8
 
PGA response at Weeks 2, 4, and 8
 
Change in PASI from Baseline at Weeks 2, 4, 8, and 12
 
% change in PASI from Baseline at Weeks 2, 4, 8, and 12
 
PASI-50 at Weeks 2, 4, 8, and 12
 
PASI-75 at Weeks 2, 4, and 8
 
PASI-90 at Weeks 2, 4, and 8
 
Change in %BSA from Baseline at Weeks 2, 4, and 8
 
% change in %BSA from Baseline at Weeks 2, 4, 8, and 12
 
	ITT, MI	ITT, OC
Other Endpoints 
 
Change from Baseline in Peak NRS at Weeks 2, 4, 6, 8, 10, 12 and 16
 
% change from Baseline in Peak NRS at Weeks 2, 4, 6, 8, 10, 12 and 16
 
Peak NRS 4-point Responder at Weeks 2, 4, 6, 8, 10, 12 and 16
 
Change from Baseline in DLQI at Weeks 4, 12, and 16
 
% change from Baseline in DLQI Total Score at Weeks 4, 12 and 16
 
Change from Baseline in PSD at Weeks 2, 4, 8, 12, and 16
 
% change from Baseline in PSD Total Score at Weeks 2, 4, 8, 12 and 16
 
Change from Baseline in SF36 at Weeks 4, 12, and 16
 
	ITT, OC	N/A

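### The daily itch difference and plot read as unadjusted, although the same SAP section adjusts itch by visit; adjusting by day is a near-free gain in precision for a descriptive display

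*SAP*

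**What the plan says.** SAP 12.8.3 handles the itch score in two ways.

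- **By visit.** Change in Peak Pruritus-NRS is analysed by ANCOVA with treatment, "baseline PGA score as a categorical covariate, and baseline value of the endpoint as a covariate". The table in SAP 12.8 gives the time points: "Change from Baseline in Peak NRS at Weeks 2, 4, 6, 8, 10, 12 and 16", in the ITT population on observed cases.
- **By day.** Diary and in-clinic itch scores "will be listed and summarized using descriptive statistics by day". The treatment difference "in mean change from baseline values and its associated 95% CI will be summarized by day", and "the treatment difference and its associated 95% CI will be plotted by day". No model, covariate or least-squares mean is mentioned.

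Where SAP 12.8.2 wants an adjusted difference, it names the ANCOVA, its covariates and the least-squares means.

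The covariates exist. In the protocol's Schedule of Assessments, both PGA and the NRS are due at Baseline, and a footnote says "Subjects should perform the Peak Pruritus NRS assessment daily". SAP 11.3 fixes the reference value: "Baseline value is defined as the last non-missing value prior to the first dose of study drug". Baseline PGA is the randomization stratum (SAP 6). Protocol 10.4.4 also specifies ANCOVA with baseline as covariate for change in Peak Pruritus-NRS, at Weeks 2, 4, 8 and 12. According to the SAP revision history, the daily itch analysis came in with Amendment 2.

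**The concern.** The daily display goes beyond a listing of means: it gives a between-arm estimate with a 95% CI for each day. Readers will use it to judge how soon and how steadily itch separates from vehicle. A raw change score subtracts the whole of one baseline reading, noise included, whatever the true slope of the daily score on baseline. Two costs follow. The intervals are wider than they need be once that slope has moved away from 1. And because the same baseline reading is subtracted on every day, a chance difference between arms in baseline itch pushes the daily points in one direction. Randomization is stratified by PGA only and the inclusion criteria set no itch threshold, so balance in baseline itch is left to chance. The SAP gives no reason for leaving out covariates that it uses two paragraphs earlier.

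**Working it through.** The plan states no figure for the daily itch display, so there is none to reproduce.

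**Inputs.** Arm sizes of about 333 and 167 and up to 25% loss by Week 12 (SAP 7). Assumptions, because the documents do not give them: baseline SD s0, daily SD s1, correlation rho between baseline and the daily score, the same in both arms; SD 2.5 NRS points where a result in points is shown.

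**Variance per subject**

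- Difference in mean change: s0² + s1² − 2·rho·s0·s1
- ANCOVA on baseline: s1²·(1 − rho²)
- Excess of the first over the second: (s0 − rho·s1)², which cannot be negative

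The excess is zero when the slope of the daily score on baseline, rho·s1/s0, equals 1.

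**Equal SDs** (divide by the common variance; the width ratio is √((1 + rho)/2))

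| rho | change score 2(1−rho) | ANCOVA 1−rho² | variance ratio | width ratio | ANCOVA CI narrower by |
|---|---|---|---|---|---|
| 0.3 | 1.40 | 0.91 | 0.65 | 0.806 | 19% |
| 0.5 | 1.00 | 0.75 | 0.75 | 0.866 | 13% |
| 0.7 | 0.60 | 0.51 | 0.85 | 0.922 | 8% |
| 0.9 | 0.20 | 0.19 | 0.95 | 0.975 | 2.5% |

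Put the other way, the unadjusted interval is about 24%, 15%, 8.5% and 2.6% wider.

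**Unequal SDs, rho from 0.2 to 0.95.** With s1/s0 = 0.8 the unadjusted interval is 25% to 47% wider. With s1/s0 = 1.2 it is 0.2% to 19% wider.

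**In NRS points** (SD 2.5, 333 and 167 subjects). Half-width unadjusted against adjusted: 0.551 and 0.445 at rho 0.3; 0.466 and 0.404 at 0.5; 0.361 and 0.333 at 0.7; 0.208 and 0.203 at 0.9. With 250 and 125 subjects (25% lost), at rho 0.5: 0.539 and 0.467.

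**Cost of the extra covariates.** A simulation with 250 and 125 subjects, PGA strata of 10/80/10% and no PGA effect on itch gave mean width ratios of 0.81, 0.87, 0.93, 0.98 and 0.99 at rho 0.3, 0.5, 0.7, 0.9 and 0.95 with equal SDs. With the slope at about 1 (rho 0.9, SD ratio 1.1) the ratio was 1.004: there ANCOVA gains nothing and pays a trivial price.

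**Chance baseline imbalance.** If the tapinarof arm starts d points higher, the difference in mean change moves by −(1 − slope)·d. The SE of the baseline difference is 2.5·√(1/333 + 1/167) = 0.237. A 2-SE imbalance is 0.474, and at slope 0.5 it moves a daily point by 0.5 × 0.474 ≈ 0.24, against an ANCOVA half-width of 0.40. At a slope near 1 the movement vanishes.

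**The case against.** The best defence is that the adjusted itch analysis is already planned by visit and that the daily table and plot are framed as descriptive. They are not in the endpoint lists, the SAP 12.8 analysis table or the fixed sequence in SAP 11.6, and no test or onset claim hangs on them. A raw difference beside raw means is an ordinary display. All of that stands, and it limits the point to an inexpensive improvement.

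A reader might infer more than the documents support:

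- **That every daily interval is materially too wide.** The loss goes to zero as the slope on baseline nears 1, which is likely in the first days. The gain is therefore probably smallest in the part of the plot used to judge onset.
- **That the plotted estimates are invalid.** Under randomization the difference in mean change is unbiased. It uses baseline, but with a fixed slope of 1, so it over-corrects an imbalance when the true slope is lower.
- **That the daily and by-visit results conflict because of the estimator, and that adjustment would make them agree.** SAP 11.4 analyses scheduled visits as nominal visits, and the Schedule of Assessments allows ±2 days (±4 at Week 16). A single study day mixes diary scores from some subjects with in-clinic scores from others. The two analyses use different data and will differ somewhat under any estimator.

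Finally, the SAP never uses the word unadjusted. That is the natural reading, not an explicit statement.

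**Conclusion.** The point holds as a matter of precision. What reads as an unadjusted daily difference gives up information that the same section uses by visit. With the same variances and correlation in both arms, its interval is never narrower than the ANCOVA interval in large samples. The gain from adjusting is about nil in the first days and about 8% to 19% of interval width once the correlation falls to 0.7 to 0.3 with equal SDs. It is larger if the daily SD shrinks below the baseline SD and smaller if it grows. Most of the gain would come from baseline NRS; what PGA adds cannot be sized from the documents. A chance baseline imbalance would also tilt the later points in a common direction, by an amount that depends on the slope. Validity is not in question, and no primary or secondary conclusion is affected.

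**What to change.** In the last paragraph of SAP 12.8.3, state that the daily treatment difference and 95% CI are the least-squares mean difference and CI from the ANCOVA already given in that section (treatment, baseline PGA category, baseline NRS), fitted separately for each day on observed cases. Plot that difference, and keep the raw daily means and mean changes as descriptive columns. A footnote should say that values on visit days need not equal the by-visit estimates, because of visit windows and the mix of diary and in-clinic scores. If the sponsor prefers the raw difference, the SAP should at least say that it is unadjusted and how its interval is computed.

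The cost is one SAP sentence and a small programming change before unblinding. No new data are needed.

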### **12.8.4 Subgroup Analyses**

The primary and all secondary efficacy endpoints will be summarized descriptively in each baseline PGA subgroup, study center, age (<65,  $\geq 65$ ), sex, race (White, Other), duration of disease (<5 Years, 5-10 Years, >10 Years), %BSA affected (<10%,  $\geq 10\%$ ) and country (USA and Canada). The %BSA Affected continuous outcome will be further explored with summaries of change and % change in %BSA Affected at Week 12 by body region. The implications of any significant heterogeneity on the assessment of overall efficacy will be explored.

## **12.9 Safety Analysis**

All safety analyses will be conducted in the Safety Population. Data will be listed by subject and treatment and summarized by treatment. No formal statistical comparisons will be made for safety data.

Single 12-lead ECGs, Hospital Anxiety and Depression Scale (HADS) collected at Screening visit will be presented in a by-subject listing.

### **12.9.1 Adverse Events**

AE terms will be coded using the MedDRA dictionary. A treatment-emergent AE (TEAE) is defined as an AE that starts after the first dose of study medication. For subjects not rolling over to Open-label study, all reported AEs will be included in the Double-Blind phase summaries. For subjects rolling over to the Open-label study, all AEs with an onset date on or before the Week 12 visit date will be included in the Double-Blind phase summaries.

If relationship to treatment is missing, the event will be conservatively treated as related to study drug. Missing severity will be imputed to the highest severity level (most severe).

All AEs will be listed by treatment and by subject, detailing the verbatim term given by the investigator, the preferred term (PT), system organ class (SOC), onset date and time, end date and time, duration (days), CTCAE grade, outcome, relationship to study drug/treatment, action taken with study drug/treatment, other action taken to treat the event, seriousness and criteria for seriousness. Serious AEs (SAEs), TEAEs leading to study discontinuation, TEAEs related to study drug will also be listed separately. The following adverse event of special interest (AESIs) will be identified and listed separately: contact dermatitis, folliculitis, and headache.

AEs will be summarized by treatment and overall as incidence rates of:

- Any AE
- Any TEAE
- Any AESIs
- Any treatment-related TEAE, including definitely, probably, and possibly related
- Any TEAE leading to study drug discontinuation
- Any SAE (non-Fatal)
- Any serious TEAE
- Death
- Treatment-related Serious TEAE
- Serious TEAE leading to study drug discontinuation

Individual PTs will be summarized by treatment according to the following:

- All TEAEs by SOC in alphabetical order and PT in descending order of combined frequency (also for treatment-related TEAEs, TEAEs leading to study discontinuation and serious TEAEs)
- All TEAEs by SOC, PT, and maximum CTCAE grade
- All TEAEs by SOC, PT, and maximum causality (not related, related) to the study drug

In addition, TEAEs and serious TEAEs will be summarized by SOC (alphabetical order) and PT (descending order) for the following subgroups:

- Age (<65 and >= 65 years old)
- Sex
- Race (White, Other)

At each level of summarization, a subject will be counted once if he/she reported one or more events. The severity of TEAEs and relationship to study drug will be summarized in a similar manner. For summaries of relationship to study drug, a subject will be classified according to the closest relationship. For summaries of TEAE CTCAE grade, a subject will be classified according to the worst grade.

For AESIs, summarization will be more extensive, reflecting the more detailed information collected. Information summarized will include number of events per subject, earliest onset day, duration (in days), causality, grade and seriousness of AESIs, outcome, actions taken with study drug, assorted physical characteristics of the AESIs, and demographic/baseline characteristics and PGA status of the subjects experiencing them. Each type of AESI will be summarized separately. If a subject has more than one treatment-emergent occurrence of an AESI, the subject's maximum duration, highest levels of causality and seriousness, maximum grade and generally the most extreme level of each characteristic will be summarized. If an AESI was ongoing at EOS, it will not be included in the duration summary.

A Kaplan-Meier figure will be generated for each AESI of time to first event. Subjects not experiencing the AESI will be censored at the date of study completion or discontinuation.

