6.3. Safety Assessments

6.3.1. Adverse Events

All AEs will be collected from the time the subject signs the ICF until the final visit/contact with the subject. Additional safety information, including the definition of an AE and the methods for recording, evaluating, and assessing causality of AEs and the procedures for completing and transmitting SAE reports are provided in [Section 8](#).

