7.1. Visit 1; Screening Period (Day -34 to Day -1)

After the subject has signed the Informed Consent Form (ICF), potential study subjects will undergo Screening procedures and assessments to confirm eligibility to participate in the study. Screening assessments will include the following:

- Demography recording
- Serum pregnancy test (females of child-bearing potential)
- Medical history recording
- ECG recording
- Brief physical examination (including weight, height, and body mass index [BMI])
- Vital signs measurements
- HADS assessment
- PGA score
- %BSA affected calculation; subject’s scalp, palms, and soles should be excluded from the %BSA calculations used to determine patient’s eligibility
- Blood sample collection for clinical laboratory tests (serum chemistry, hematology, diagnostic tests)
- Urinalysis
- AE recording (from the time the ICF is signed)
- Concomitant medication recording (from the time ICF is signed)

To determine subject eligibility at Screening, a single repeat of tests or procedures may be allowed at the discretion of the Investigator. The Medical Monitor should be consulted if needed.

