8.1.1. Definition of Adverse Events

An AE is any untoward medical occurrence in a Subject temporally associated with the use of a medicinal product, whether considered causally related or not related to the medicinal product.

An AE can therefore be any unfavorable and unintended sign (including an abnormal laboratory finding), symptom, or disease (new or exacerbated) temporally associated with the use of a medicinal product.

Events meeting the definition of an AE **include**:

- Any abnormal laboratory test results (hematology, clinical chemistry) or other safety assessments (eg, vital signs measurements), including those that worsen from baseline, and felt to be clinically significant in the medical and scientific judgment of the Investigator
- Exacerbation of a chronic or intermittent pre-existing condition (eg, atopic dermatitis) including either an increase in frequency and/or intensity of the condition
 - For skin-related AEs, it should be noted whether or not the event is in the area of active application of study drug, and/or if spreading beyond the application site.
- New conditions detected or diagnosed after study drug administration even though it may have been present prior to the start of the study
- Signs, symptoms, or the clinical sequelae of a suspected interaction
- Signs, symptoms, or the clinical sequelae of a suspected overdose of either study drug or a concomitant medication (overdose per se will not be reported as an AE/SAE)
- "Lack of efficacy" or "failure of expected pharmacological action" per se will not be reported as an AE or SAE. Such instances will be captured in the efficacy assessments. However, the signs, symptoms, and/or clinical sequelae resulting from lack of efficacy will be reported as AE or SAE if they fulfill the definition of an AE or SAE.
- Symptomatic complaints at the site of local application (eg, burning/stinging, pruritus, and erythema)

Events that **do not** meet the definition of an AE include:

- Any clinically significant abnormal laboratory findings or other abnormal safety assessments that are associated with the underlying disease, unless judged by the Investigator to be more severe than expected for the subject's condition
- The disease/disorder being studied or expected progression, signs, or symptoms of the disease/disorder being studied, unless more severe than expected for the subject's condition

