8.3. Time Period and Frequency for Event Assessment and Follow-Up

8.3.1. Adverse Event Reporting

All AEs will be collected from the time of signed informed consent until the final visit.

Any AEs assessed as related to study participation (eg, protocol-mandated procedures, invasive tests, or change in existing therapy) will be collected from the time a subject consented to participate in the study up to and including any follow-up contact.

All SAEs will be recorded in the eCRF and reported to the Sponsor within 24 hours via email or phone (refer to Medical Monitor/Sponsor Information page for contact information) (see Section 8.4).

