8.3.2. Follow-Up of Adverse Events

After the initial AE/SAE report, the Investigator is required to proactively follow each subject at subsequent visits/contacts. All SAEs and nonserious AEs will be followed until resolution, until the condition stabilizes, until the event is otherwise explained, or until the subject is lost to follow-up.

The Investigator will assess the outcome of each AE using the following criteria:

- **Recovered/Resolved:** The event has improved or subject recuperated.
- **Recovered/Resolved with sequelae:** The subject has recuperated but retained pathological conditions resulting from the prior disease or injury.
- **Recovering/Resolving:** The event is improving.
- **Not recovered/Not resolved:** The event has not improved or subject recuperated.
- **Unknown:** The outcome of the event is not known, not observed, not recorded, or refused.
- **Fatal:** Termination of life as an outcome of the AE.

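### The TEAE definition in SAP 12.9.1 does not cover AEs that begin before the first dose and worsen on study drug, and no rule says such worsening is entered as a new AE

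*SAP*

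**What the plan says.** **Definition.** SAP 12.9.1 (Adverse Events): "A treatment-emergent AE (TEAE) is defined as an AE that starts after the first dose of study medication". The test is the start date alone. Protocol 10.4.3 (Safety Analyses) limits its AE summaries by the same time rule and is equally silent on worsening.

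**Collection.** Protocol 8.3.1: "All AEs will be collected from the time of signed informed consent until the final visit". Protocol 6.3.1 agrees, and protocol 7.1 places screening at Day -34 to Day -1.

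**Worsening.** Protocol 8.1.1 lists as an adverse event "Exacerbation of a chronic or intermittent pre-existing condition (eg, atopic dermatitis) including either an increase in frequency and/or intensity of the condition". The same section excludes expected fluctuations of conditions present at study start only if they do not worsen.

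**Follow-up and recording.** Under protocol 8.3.2, after the initial report "the Investigator is required to proactively follow each subject at subsequent visits/contacts", and events are followed until they resolve, stabilise or are otherwise explained. For each event, the SAP 12.9.1 listing shows, among other items, "onset date and time, end date and time, duration (days), CTCAE grade".

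**The concern.** The period in which events are recorded opens at consent, but the treatment-emergent classification looks only at whether the recorded onset falls after the first dose. Take an event that starts at Grade 1 in screening, is still present on Day 1, and reaches Grade 3 in Week 3. Clinically, the on-treatment change is what a TEAE table is meant to show. Under a pure start-date rule, whether it is shown depends on how the site enters it.

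TEAE incidence, frequency and duration is a named safety endpoint (protocol Section 2), and the study is intended to support registration (protocol 1.1.2). A related Grade 3 event is also a ground for stopping study drug under protocol 4.6.1. The events at risk of being missed therefore include ones that could end treatment. Two sites could record the same course differently and produce different TEAE counts.

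**Working it through.** The point concerns a definition, and the plan gives no figure to reproduce. The check sets the rules side by side and traces one event through them.

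**Step 1. Can pre-dose events be on file?** Yes. Collection starts at consent (protocol 6.3.1, 8.3.1) and screening may last up to 34 days (protocol 7.1).

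**Step 2. Do the documents say how worsening is recorded?** No.
- Protocol 8.1.1 makes an exacerbation of a pre-existing condition an adverse event. It does not say that an event already recorded after consent gets a second, newly dated record when it worsens.
- Protocol 8.3.2 requires continued follow-up. That fits updating the existing record, but does not require it.
- One onset date and one grade per listed event (SAP 12.9.1) fits either practice.

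**Step 3. Trace the event.** Onset is in screening, with worsening after the first dose and on or before the Week 12 visit.

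| SAP 12.9.1 output | One record, pre-dose onset kept | New record dated at worsening |
|---|---|---|
| Any-TEAE row | not counted | counted |
| TEAE tables by SOC/PT, maximum grade and causality; age, sex and race subgroups | not counted | counted |
| Rows and tables for treatment-related TEAEs, serious TEAEs and TEAEs leading to discontinuation | not counted | counted where applicable |
| Listings of related TEAEs and of TEAEs leading to study discontinuation | absent | present where applicable |
| Any-AE row and listing of all AEs | present | present |
| Any-AESI row (contact dermatitis, folliculitis, headache) | present as written | present |
| SAE row (non-fatal) and SAE listing | present if serious | present if serious |

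A subject with another TEAE still enters the any-TEAE row through that event. The specific term, grade or causality would still be missing.

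**Step 4. Direction.** The single-record practice removes events from TEAE outputs and adds none, so it can only lower TEAE counts, in either arm. The SAP's other conventions lean the opposite way. Missing relationship counts as related and missing severity as the most severe (12.9.1), and a completely missing start date counts as treatment-emergent (Section 9).

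**Step 5. Scale per subject.** At the planned group sizes, one omitted subject changes an incidence by 1/333 = 0.30 percentage points on tapinarof, or 1/167 = 0.60 on vehicle. The number of such subjects would be (subjects with an AE ongoing at Day 1) × (fraction worsening on drug) × (fraction kept on one record). The documents give none of the three, so no total is offered.

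**Step 6. AESI outputs.** The any-AESI row is separate from the any-TEAE row and carries no treatment-emergent limit. The detailed AESI summary uses that term only in its rule for subjects with several occurrences. The Kaplan-Meier text states neither such a limit nor a time origin. If time runs from the first dose, a pre-dose AESI would have an event time before zero, so the intended scope needs stating.

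**The case against.** The strongest reply is that protocol 8.1.1 already treats an exacerbation as an adverse event in its own right. On a plain reading, on-drug worsening is then a new event with a post-dose onset and meets the existing definition. The data-entry convention would sit in eCRF completion guidance, which is not part of these documents. This stands to the extent that a reader might infer such events are certain to be lost. The documents do not support that; the loss depends on how sites record the worsening. It does not close the gap, because no passage requires a new record.

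A reader might also infer that the AESI tables leave these events out. The text does not support that either: the any-AESI row would include them, and the detailed AESI text is only ambiguous. Headache is also a limited example. A fresh episode after dosing has its own onset and counts as a TEAE already, so only a headache continuing across Day 1 is exposed.

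The events would not be hidden, since the any-AE row, the full listing and the SAE outputs retain them, and no formal safety comparison is planned (SAP 12.9). This limits the harm. However, the SOC/PT tables are built on TEAEs, so the worsening would be visible only subject by subject.

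Finally, if the database holds one onset and one grade per event, a worsening flag cannot be derived from those fields alone. That is correct, so the definition must be paired with a recording rule and a data check.

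**Conclusion.** The point holds in conditional form. The SAP's TEAE definition does not address events that start before the first dose and worsen after it, and neither document says how that worsening is recorded. Where a site keeps a single record, the event drops out of every TEAE output, and the resulting error can only be an understatement.

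The size cannot be estimated from the documents. A reader might infer a specific shortfall on tapinarof, or a bias between arms. Neither is supported: no rate of pre-dose or worsening events is given, and the same rule applies to vehicle. The tapinarof-vehicle difference would be understated only if such omissions were proportionally more frequent on tapinarof, which the documents do not show.

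The conclusion assumes that no eCRF guidance outside these documents already requires a new record. If it does, the remaining need is to state that rule in the SAP and settle the AESI scope. The correction is worth making because the endpoint is a named one and the change is small.

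**What to change.** 1. In SAP 12.9.1, define a TEAE as an AE that starts after the first dose, or that started before it and increases in CTCAE grade or becomes serious after it.
2. State the recording rule: worsening of this kind is entered as a new AE record dated at the worsening. Put the same line in the eCRF guidance.
3. For data already collected, identify AEs ongoing at Day 1 during blinded data review before database lock. Query sites for any later worsening and its date where the record does not show it.
4. State whether the detailed AESI summaries and the AESI Kaplan-Meier figures are limited to treatment-emergent events.

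The cost is a few sentences, one derived flag and a short data check. TEAE counts may become slightly less favourable.
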